6.2 SECONDARY OBJECTIVES

6.2.1 SECONDARY OBJECTIVE 1

To estimate whether antibody responses to all 4 vaccine antigens are greatest in participants who received QIV-R and least in participants who received QIV-E, and if this reflects greater cell- to egg-grown antibody titre ratios.

Corresponding outcomes:

1. Post vaccination trend in GMT QIV-R > QIC-C > QIV-E
2. Post-vaccination seropositivity and trend in seropositivity of QIV-R > QIC-C > QIV-E
3. Pre- to post-vaccine mean fold-rise in GMT (~ Geometric Mean Ratio (GMR)) and trend in fold rise of QIV-R > QIC-C > QIV-E
4. Post-vaccination seroconversion and trend in the proportion who have seroconverted of QIV-R > QIC-C > QIV-E

6.2.2 SECONDARY OBJECTIVE 2

To estimate whether QIV-R induces antibodies against a greater genetic and antigenic range of A(H3N2) viruses than QIV-C and QIV-E.

Corresponding outcomes:

1. Breadth of antibodies induced by vaccination as measured through pre-vaccination, post-vaccination and post-season serum samples tested against a landscape panel of approximately 30 influenza A(H3N2) strains that have circulated since 1968.

6.2.3 SECONDARY OBJECTIVE 3

To estimate whether prior vaccination history has less effect on antibody responses induced against all 4 vaccine antigens by QIV-R compared with QIV-C and QIV-E.

Corresponding outcomes:

For each vaccine type and vaccination history group (frequently versus infrequently vaccinated) compare:

1. Post-vaccination GMT
2. Post-vaccination seropositivity
3. Post-vaccination fold-rise in geometric mean antibody titre (GMT)
4. Post-vaccination seroconversion fraction
5. Post-vaccination antibody breadth (proportion of landscape antigens with GMT>40)

6.2.4 SECONDARY OBJECTIVE 4

To estimate whether antibody titres against all 4 vaccine antigens are better maintained up to 12 months after vaccination with QIV-R compared with QIV-C and QIV-E

Corresponding outcomes:

1. Post-season GMT
2. Post-season seropositivity
3. Proportion of landscape antigens (as per Objective 2) with GMT>40 post-season

6.2.5 SECONDARY OBJECTIVE 5

To estimate whether QIV-R induces higher frequencies of HA reactive B cells and/or B cells with different HA cross-reactivity profiles and phenotypes compared with QIV-C and QIV-E.

Corresponding outcomes:

1. Heterogeneity of antibody generating B cells in terms of phenotype and reactivity against a panel of well-defined recombinant hemagglutinin probes that represent a range of influenza A(H3N2) virus clades.

6.2.6 SECONDARY OBJECTIVE 6

To assess whether QIV-R offers better protection against infection compared with QIV-C or QIV-E.

Corresponding outcomes:

1. Attack rates in each vaccination group
2. Post-vaccination GMT in infected versus uninfected participants for each vaccination group
3. Characterisation of antibody and B cell responses

7 MONITORING OF CLINICAL SYMPTOMS AND SEQUENCING OF INFLUENZA STRAINS

7.1 STUDY DESIGN

The proposed study is a single season randomized, modified investigator and participant blind study (participants & staff blinded except for clinical trial nurse) clinical trial of 360 adults aged 21-49 years with 3 arms comparing 3 vaccines. Randomisation will be stratified by vaccination history, frequently vaccinated vs. infrequently vaccinated, to compare the responses to each vaccine (Figure 1):

Group A – frequently vaccinated:

1. QIR-R
2. QIV-E
3. QIV-C

Group B –infrequently vaccinated:

4. QIR-R
5. QIV-E
6. QIV-C

[figure not shown]

Figure 1. Randomization schema. QIV-E: egg-based quadrivalent influenza vaccine; QIV-C: cell-based quadrivalent influenza vaccine; QIV-R: recombinant quadrivalent influenza vaccine

7.2 JUSTIFICATION OF THE STUDY DESIGN

The objectives of this study will be to assess whether vaccination with QIV-R results in a better immune response towards vaccination compared with either QIV-E or QIV-C.

The vaccines QIV-C and QIV-R used in this study are not licensed in Singapore. However, given the acceptable safety data generated from the millions of doses of QIV-R administered in the USA (under the tradename Flublok Quadrivalent), and the fact that this product will be sourced from the US, we consider that the risk/benefit ratio is appropriate for the conduct of a clinical study with QIV-R.

Some data already exist comparing QIV-R with QIV-E and QIV-C; however early formulations (pre-2013) of QIV-R were susceptible to the formation of disulphide cross-links, resulting in decreased potency during storage (loss of up to 50% potency). This was rectified through the addition of low concentrations of a reducing agent, sodium thioglycolate (STG), in combination with citrate that reduced the rate of potency loss by up to 20-fold (15, 16). HA instability would have led to suboptimal vaccine being used in clinical trials pre-2014 and could explain the initial need for an increased antigen load (45ug / strain), it could also explain why earlier results failed to show any obvious superiority over traditional vaccines. Therefore, new data are required to assess the immunogenicity of this QIV-R over QIV-E and QIV-C.

In addition, investigations to-date have largely only examined antibody titres against the vaccine antigen, and have mostly not considered vaccination history. We will investigate the whether the breadth of antibody responses varies among formulations and whether responses against each vaccine are similarly affected by prior vaccination. Prior studies, by ourselves and others, found that vaccine immunogenicity was clearly attenuated among participants who had been vaccinated during three or more of the preceding 5-years, not attenuated among participants who have one prior vaccination, and somewhat attenuated among participants with two prior vaccinations. Therefore, in this study, we will compare the immunogenicity of each vaccine among infrequently versus frequently vaccinated participants, defined as having 0-1 versus 3+ vaccinations during the preceding five-years. Participants who have been vaccinated twice will be excluded. The number of prior years considered is a pragmatic choice made to minimize the number of years that participants are asked to recall their vaccination status, while still allowing participants to be stratified into groups that are anticipated to have different vaccine immunogenicity. Participants who would normally be vaccinated

annually may have missed vaccinations during 2020-21 due to the COVID-19 pandemic, but would still be classified as highly vaccinated (3+) vaccines if vaccination status over 5-years is considered.

Lower age limit for study participants will be 21 years per the age of majority in Singapore as provided by common law.

7.3 STUDY SCHEDULE

Assessment/Procedure	Screening	Visit 1 (V1) (prior to vaccination)	Visit 2 (v2) (14 days post vaccination)	Visit 3 (V3) (6 months post vaccination)	Visit 4 (V4) (12 months post vaccination)
Study timeline	Day 0	Day 1	Day 14	Day 150	Day 330
Time window	-28 to 1d	NA	+7d	±30d	±30d
Informed Consent	X				
Collection of demographic information	X				
Weight and height measurement	X				
History of seasonal influenza vaccination	X				
Randomization	X				
Blood Collection	X ^a	X ^a	X	X	X
Vaccination		X			
Immediate surveillance (15 min)		X			
ARI surveillance^b		D14-D360			
Swab collection^b		D14-D360			
Study termination record					X
Collection of SAEs and AESIs^d	Throughout study				

AESI = adverse event of special interest, SAE = serious adverse event; ARI: acute respiratory infection

- Collection of the first blood sample to occur before vaccination, and may be taken at Screening or Visit 1 if the blood draw is not possible for one reason or another. The study team will make every effort to complete all blood-taking in one seating to avoid pricking the participants more than once.
- Subjects will be contacted weekly by SMS to record information about acute respiratory infections and prompted to collect a nasal swab if symptomatic.
- AESIs will have the same detailed information collected as SAEs. These include new onset of Guillain-Barré syndrome, encephalitis/myelitis (including transverse myelitis), Bell's palsy, optic neuritis, and brachial neuritis.

Study Name: Immunogenicity trial of 3 influenza vaccine [VAP3]

Protocol Number: 2021.247

DSRB Ref Number: 2022/00275

Version & date: version 2.0, dated 27 Oct 2022

Page 16 of 38

7.4 VACCINATION

Participants will be randomized as they are recruited to receive a single injection of one of the 3 vaccines. QIV-R is currently only manufactured to contain influenza virus strains recommended for use in northern hemisphere Influenza Vaccines. Therefore, all vaccines used in this study (QIV-R, QIV-E, QIV-C) will be northern hemisphere vaccines.

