9.2 RANDOMISATION AND ALLOCATION PROCEDURES

Randomisation to vaccine group is stratified based on history of vaccination. Consenting participants will be identified as being in either the infrequently vaccinated group (0 or 1 prior vaccinations) or the frequently vaccinated group (3 or more prior vaccinations) and subsequently randomized within each stratum (see Figure 1)

A computer-generated randomization list will be used for labelling and packaging of doses.

Within each vaccination history stratum (frequently and infrequently vaccinated), subjects who meet the inclusion/exclusion criteria and provide informed consent will be randomly assigned to one of the 3 vaccine groups (QIV-R, QIV-E or QIV-C) in a 1:1:1 ratio. A second round of randomization will be used to assign participants in each of the 6 groups for collection of additional blood tubes in a ratio of 1:2 (1/3) until a target of 20 per group.

Site staff will enter the identification information into REDCap and confirm a minimal amount of data. The unblinded research fellow will perform the randomisation on REDCap. Both the unblinded research fellow and vaccination nurse will have access to the randomisation results on REDCap. Before administering the vaccine, the nurse vaccinator will check the vaccine group allocated to the participant by referring to the REDCap randomisation results and have the site administrator confirm it. The full detailed procedures for group allocation will be described in the manual of procedures.

If a subject is not eligible to participate in the study, then the information will only be recorded on the screening/enrolment log.

Subject numbers that are assigned by REDCap will be unique for each screened potential participant. Subject numbers will not be reassigned for any reason. The randomization codes will be stored securely in REDCap.

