11 STUDY POPULATION

11.1 INCLUSION CRITERIA

Eligible participants will be recruited from staff members of NCID, TTS defence and the general public by hospital/University newsletters, social media posts/advertising, emails and the study website, as permitted. Participants will meet the following criteria:

- Aged ≥ 21 years and ≤ 49 years.
- Able to provide informed consent
- Willing and able to provide 4 blood samples:
 - a. just prior to vaccination (V1),
 - b. 14–21 days post vaccination (V2)
 - c. 4–6 months post-vaccination (V3)
 - d. 10–12 months post-vaccination (V4).
- Has not received influenza vaccine for at least 6 months¹
- Willing to provide current mobile phone number for SMS reminders

¹ To maximise the recruitment of healthcare workers before the year-end flu vaccination exercise (Oct-Dec period), participants who have received their influenza vaccine less than 6 months ago may be enrolled but their vaccination visit and blood sample collection will be scheduled at least 6 months after their last influenza vaccine dose.

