11.2 EXCLUSION CRITERIA

- Known contraindication(s) for QIV (e.g. hypersensitivity to vaccine component (including eggs)).
- Recently (last 7 days) or currently ill or has a fever above 38°C.
- Cannot recall if they were vaccinated against influenza during more or less than two of the preceding five years. Vaccinated during two of the preceding five years.
- Hypogammaglobulinaemia on immunoglobulin replacement
- Undergoing immuno-suppressive therapies including corticosteroids²

2 Received systemic immunosuppressants or immune-modifying drugs for >14 days in total within 6 months prior to Screening (for corticosteroids \geq 20 milligram per day of prednisone equivalent). Topical tacrolimus is allowed if not used within 14 days prior to Day 1. Individuals who are immunocompromised (e.g. active leukemia or lymphoma, generalised malignancy, aplastic anaemia, solid organ transplant, bone marrow transplant, current radiation therapy congenital immunodeficiency, HIV/AIDS with CD4 lymphocyte count < 200).

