11.3 RECRUITMENT PROCEDURES

The study will seek to recruit hospital staff working at NCID, TTS defence and the general public. It will be promoted via poster advertisements, as well as sharing of digital copies of the poster via emails and on NCID/TTS defence and/or A*STAR websites (Attachment 1 and 2). Participants who are interested in participating in the study may directly contact the study team via the contact details provided on the advertising poster.

A study team member will go through the eligibility criteria and informed consent procedures. Baseline data collection and blood draws will take place in a private location located in or adjacent to the clinic. To facilitate recruitment, the baseline blood draw may occur up to four weeks prior to vaccination.

The recruitment of infrequently vaccinated people will be reinforced by using the “snowball sampling” strategy in which existing study participants can refer other potential participants from among their acquaintances.

Participants will be reimbursed 50\$ at each visit for their time and travel costs.

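### Randomisation is scheduled at Screening, up to 28 days before vaccination, so participants can be lost after allocation and before injection with no primary outcome

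*Combined protocol and SAP*

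**What the plan says.** The schedule in section 7.3 has one row, "Randomization", with a single mark under Screening. The Screening window is -28 to 1 d, and vaccination is marked only at V1. Section 7.4 agrees: "Participants will be randomized as they are recruited to receive a single injection of one of the 3 vaccines". Section 11.3 explains the lead time: "To facilitate recruitment, the baseline blood draw may occur up to four weeks prior to vaccination".

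Section 9.2 sets the condition for allocation: "subjects who meet the inclusion/exclusion criteria and provide informed consent will be randomly assigned to one of the 3 vaccine groups". It adds that "Both the unblinded research fellow and vaccination nurse will have access to the randomisation results on REDCap". The check it describes before injection is of the allocated vaccine group. A second randomisation, within each of the six vaccine-by-history groups, picks the participants who give heparin tubes, to a target of 20 per group.

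Some criteria can change with time. Section 11.2 excludes anyone "Recently (last 7 days) or currently ill or has a fever above 38°C" and names no reference visit. Section 11.1 requires at least 6 months since the last influenza vaccine, and its footnote 1 says that recently vaccinated people "may be enrolled but their vaccination visit and blood sample collection will be scheduled at least 6 months after their last influenza vaccine dose".

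Section 12.3 says all participants will be analysed, and section 12.4 says the team will try to replace those who miss V2. ITT and PP appear only in the glossary. No rule covers a participant who is randomised and never vaccinated.

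**The concern.** The primary outcome is a post-vaccination A(H3N2) titre, so it exists only for people who are vaccinated and bled at V2. If allocation comes days or weeks before injection, a participant who falls ill, is vaccinated elsewhere or does not return has already been randomised and leaves the comparison as a post-randomisation loss. Vaccination elsewhere is foreseeable, because footnote 1 refers to a year-end staff vaccination exercise. Had allocation been made at V1, the same person would simply never have been randomised.

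Two things are at stake. The first is power, if losses are similar across arms. The second is the protection that randomisation gives, if losses differ by arm and relate to titre. The second is possible because some staff already know the allocation when the participant arrives at V1. Replacing people who miss V2 restores numbers but does not restore the randomised comparison.

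**Working it through.** **1. Timing.** In section 7.3 randomisation is at Screening (day -28 to day 1) and vaccination is at V1 (day 1). The gap runs from same-day to about 28 days. Early allocation also has a function. The heparin subset is drawn within vaccine-by-history groups, and baseline blood may be taken at Screening, so for those participants the vaccine allocation must exist before the draw.

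**2. The plan's own power.** Inputs are from section 13.3: effect b_R = 0.5, error SD 1, baseline N(3.7, 1), slope 0.8, titres grouped in two-fold intervals and analysed at midpoints, 5000 runs, one-sided alpha 0.05. Re-simulating that model gives:

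| n per cell | Plan, one-sided | Re-simulated |
|---|---|---|
| 50 | 0.772 | 0.779 |
| 55 | 0.810 | 0.802 |
| 60 | 0.832 | 0.829 |

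The plan's figures are reproduced to within 1 point.

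**3. Room for loss.** Section 13.2 needs 55 per cell and recruits 60. The margin is 60 - 55 = 5 per cell, or 5 x 6 = 30 of 360 (8.3%), for all attrition up to V2. The stated 10% attrition leaves 60 x 0.9 = 54.

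**4. Power under loss unrelated to arm** (loss rates assumed, same simulation):

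| Total loss | Evaluable per cell | One-sided power |
|---|---|---|
| 10% | 54 | 0.806 |
| 15% | 51 | 0.788 |
| 20% | 48 | 0.764 |
| 25% | 45 | 0.731 |

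Simulation error is about sqrt(0.8 x 0.2 / 5000) = 0.006, which is why 54 and 55 per cell are not distinguishable here. If 2% to 8% were lost between allocation and injection (assumed), that is 0.02 x 360 = 7 to 0.08 x 360 = 29 people.

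**5. Selective loss** (illustration only). Suppose a fraction f of one of the two groups compared is lost, and the lost differ from those retained by d log units after adjustment. Then bias = f x d, and one-sided error = 1 - Phi(1.645 - bias/SE), with SE about 0.20 from the simulation at 55 per cell.
- f = 2%, d = 0.5: bias 0.01, error 0.055.
- f = 5%, d = 1: bias 0.05, error 0.082.
- f = 10%, d = 1: bias 0.10 (20% of b_R), error 0.126.

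The documents give neither f nor d.

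**6. Effect of later allocation on the heparin subset.** Suppose 60 of 180 per history stratum were chosen without regard to vaccine. The count per vaccine group would then have mean 20 and variance 60 x (1/3) x (2/3) x (120/179) = 8.9, so SD about 3 (roughly 14 to 26 at 2 SD). If vaccine is instead block-randomised 1:1:1 within subset status, 60/3 = 20 per group is kept, apart from any incomplete last block.

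**The case against.** The case for leaving the plan alone has several sound parts.

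- Twenty-eight days is a maximum. Same-day screening and vaccination is allowed, and the nominal timeline is day 0 then day 1.
- A reader might infer from footnote 1 that some people are randomised months before vaccination. The footnote speaks of enrolment, not randomisation. Section 9.2 randomises only those who meet the criteria, and a gap of months would not fit the 28-day window. The documents do not say when these people are randomised, which is a matter for reconciliation.
- A reader might also conclude that eligibility is not re-checked. That rests on silence: the schedule has no eligibility row at any visit, Screening included. The topical tacrolimus clause in section 11.2 is tied to Day 1, which implies some assessment then, and section 9.2 leaves full allocation procedures to a manual.
- Selective exclusion by the vaccinator is not documented. Section 11.3 gives eligibility to a study team member, section 9.2 gives the nurse no power to exclude or postpone, and section 9.1 blinds the investigator and the staff who collect adverse event data.
- A participant who is ill at V1 might be rescheduled and still provide a V2 titre. Even the assumed 8% loss (29 people) is inside the margin of 30.

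These points limit the size of the problem and rule out any claim that bias has been shown. The sequence remains: allocation comes first, an interval of up to 28 days may follow, and only then is the participant injected. The tacrolimus clause is not a general check at V1. The manual is cited for group allocation, not for confirming eligibility. The margin of 30 also has to cover people who are vaccinated and then miss V2.

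**Conclusion.** The point holds as an avoidable weakness in the order of procedures. The plan allows loss between allocation and injection, with the allocation already open to the unblinded fellow and nurse and no V1 eligibility confirmation described. Those lost have no primary outcome, and no rule says how they are handled.

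The likely size is modest. If loss is unrelated to arm, one-sided power is about 0.81 at 10% total loss and 0.79 at 15%. If loss is selective, the one-sided error could rise from 0.05 to between about 0.055 and 0.126 over the range shown, but that range rests wholly on assumed inputs. No figure in the plan is shown to be wrong by this point, and the documents do not establish that exclusions would be selective or that gaps would run to months.

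**What to change.** In section 7.3 move the randomisation mark from Screening to V1, and align sections 7.4 and 9.2. At V1, blinded staff confirm and record the existing eligibility criteria; the unblinded fellow then allocates in REDCap immediately before injection. Screening keeps consent, history and, where wanted, the baseline draw.

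For participants bled at Screening, select the heparin-tube subset there within vaccination-history stratum. Then block-randomise vaccine within history stratum by subset status, so that 20 per group is kept.

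Separately, reconcile footnote 1 of section 11.1, the -28 d window in section 7.3 and the synopsis, which counts the 6 months back from enrolment. State when recently vaccinated enrollees are randomised.

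The cost is a change to the schedule table and the manual, one more stratification factor in REDCap (2 x 2 = 4 strata), and allocation work on the vaccination day. Section 9.2 already has the fellow randomise in REDCap, so no new system is needed.

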7.4.1 QIV-R (FLUBLOK®) BY IM ROUTE AT V1 (D0)

FluBlok is manufactured by Sanofi-Aventis. In the United States, it is registered for use in people aged ≥ 18 years. Administration is by intramuscular injection. The vaccine antigens are manufactured synthetically and recombined with a baculovirus that infects insects. The recombinant virus is grown in bulk in a qualified insect cell line. Each 0.5mL monodose pre-filled syringe contains 45 μ g haemagglutinin of each of antigen.

7.4.2 QIV-C (FLUCELVAX® QUAD) BY IM ROUTE AT V1 (D0):

Flucelvax Quad is a registered vaccine manufactured by Seqirus for use in people aged ≥ 9 years. Administration is by intramuscular injection. The vaccine antigens are prepared in a qualified cell line. Each 0.5 mL monodose pre-filled syringe contains 15 μ g haemagglutinin of each of the 4 recommended influenza virus strains. Product advice also indicates it may contain traces of propiolactone, cetyltrimethylammonium bromide and polysorbate 80.

7.4.3 QIV-E (FLUARIX) BY IM ROUTE AT V1 (D0)

Fluarix is a registered vaccine manufactured by GlaxoSmithKline (GSK) in Germany for use in people aged ≥ 6 mths and older. Administration is by intramuscular injection. The vaccine antigens are prepared in a pathogen-specific free embryonated hens eggs. Each 0.5 mL monodose pre-filled syringe contains:

- 15 μ g haemagglutinin of each of the 4 recommended influenza virus strains
Other ingredients:
 - polysorbate 80 • octoxinol 10 • dl-alpha-tocopheryl acid succinate • sodium chloride • dibasic sodium phosphate dodecahydrate • monobasic potassium phosphate • potassium chloride • magnesium chloride hexahydrate • water for injections • ovalbumin (≤ 0.05 micrograms) • formaldehyde (≤ 5 micrograms) Traces of: hydrocortisone (trace) • gentamicin sulphate(trace) • sodium deoxycholate (trace)

